5.1 Contraception requirements

Women of childbearing potential are eligible for this study if they use highly effective methods of contraception during dosing and for 6 months after stopping study medication. Highly effective contraception methods include:

- Total abstinence (when this is in line with the preferred and usual lifestyle of the subject. Periodic abstinence (e.g., calendar, ovulation, symptothermal, post-ovulation methods) and withdrawal are not acceptable methods of contraception.

- Female sterilization (surgical bilateral oophorectomy with or without hysterectomy), total hysterectomy or tubal ligation at least six weeks before taking study treatment. In case of oophorectomy alone, only when the reproductive status of the woman has been confirmed by follow up hormone level assessment.
- Male sterilization (at least 6 months prior to screening). For female subjects in the study, the vasectomized male partner should be the sole partner for that subject.
- Use of oral, injected or implanted hormonal methods of contraception or placement of an intrauterine device (IUD) or intrauterine system (IUS) or other forms of hormonal contraception that have comparable efficacy (failure rate <1%), for example hormone vaginal ring or transdermal hormone contraception. In case of use of oral contraception, women should be stable on the same contraceptive medication for a minimum of 3 months before taking study treatment.

Men are not required to use contraception because of the large size of the antibody which does not penetrate the blood-testes barrier.

Women of child bearing potential must be informed that taking the study treatment may involve unknown risks to the fetus if pregnancy were to occur during the study, and agree that in order to participate in the study they must adhere to the contraception requirement for the duration of the study. If there is any question that the subject will not reliably comply, they should not be entered or continue in the study.

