Key Exclusion criteria	
 • Pregnant or nursing (lactating) women, where pregnancy is defined as the state of a female after conception and until the termination of gestation confirmed by a positive hCG laboratory test. • Women of child-bearing potential, defined as all women physiologically capable of becoming pregnant, unless they are using highly effective methods of contraception during dosing and for 6 months after stopping of investigational drug. • Diabetes other than type 2 such as type 1 diabetes, surgically induced-diabetes; "brittle" type 2 diabetes as per investigator judgment, history of severe hypoglycemic episodes in the year preceding screening, or hypoglycemic unawareness. 
Company Confidential Information

Study treatment	
 • Bimagrumab (BYM338) • Placebo

Efficacy/PD assessments
	
 • DXA scan for whole body, trunk, appendicular fat and lean mass • HbA1c, HOMA2-IR, QUICKI and Matsuda Index for glycemic response • Anthropometric measurement of fat by weight, body mass index (BMI), waist circumference; hip circumference; waist to hip ratio 
Company Confidential Information

Key safety assessments
	
 • Adverse events • Physical exam • Vital signs • Laboratory evaluations • ECG • Urinalysis

Other assessments
	
 • PK samples Company Confidential Information • IG (immunogenicity) Company Confidential Information • Dietary intake – including but not limited to total calories, protein, fat, carbohydrate. Company Confidential Information

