After completion of the treatment period, subjects will have a follow-up period of 8 weeks with regular monitoring for safety and efficacy beginning at Week 48 and continuing until the end of study visit (EOS) which will take place 12 weeks after the last study drug administration. The specific assessments for the follow up and end of study visits are detailed in [Section 8.1](#) (Assessment schedule).

Figure 3-1 Study design

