4.2 Exclusion criteria

Conditions related to safety:

1. Pregnant or nursing (lactating) women, where pregnancy is defined as the state of a female after conception until the termination of gestation, and confirmed by a positive hCG laboratory test at screening.
2. Women of child-bearing potential, defined as all women physiologically capable of becoming pregnant **unless** they are using highly effective methods of contraception during dosing and for 6 months after stopping of investigational drug. **Highly effective contraception methods include:**
 - Total abstinence from heterosexual intercourse (when this is in line with the preferred and usual lifestyle of the subject). Periodic abstinence (e.g. calendar, ovulation, symptothermal, post-ovulation methods) and withdrawal are not acceptable methods of contraception.
 - Female sterilization (surgical bilateral oophorectomy with or without hysterectomy), total hysterectomy or tubal ligation at least six weeks before taking investigational drug. In case of oophorectomy alone, only when the reproductive status of the woman has been confirmed by follow up hormone level assessment.
 - Male sterilization (at least 6 months prior to screening). For female subjects in the study, the vasectomized male partner should be the sole partner for that subject.
 - Use of oral, injected or implanted hormonal methods of contraception or placement of an intrauterine device (IUD) or intrauterine system (IUS) or other forms of hormonal contraception that have comparable efficacy (failure rate <1%), for example hormone vaginal ring or transdermal hormone contraception.

In the case of oral contraception, women should be stable on the same pill for a minimum of 3 months before taking the investigational drug.

Women are considered post-menopausal and not of child-bearing potential if they have had 12 months of natural (spontaneous) amenorrhea with an appropriate clinical profile (e.g. age-appropriate, history of vasomotor symptoms) or have been sterilized as specified above.

3. Any chronic active infection (e.g., HIV, hepatitis B or C, tuberculosis, etc) or has received anti-HCV treatments within the previous 6 months. Patients receiving chemoprophylaxis for latent tuberculosis infection are eligible for the study.
4. History of or known hypersensitivity to monoclonal antibodies or drugs similar to the study drug.

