7.1 Study completion and post-study treatment

Each subject will be required to complete the study in its entirety and thereafter no further study treatment will be made available to them. Study completion is defined as when the last subject completes their Study Completion visit, and any repeat assessments associated with this visit have been documented and followed-up appropriately by the Investigator, or in the event of an early study termination decision, the date of that decision.

If subjects discontinue early and are not able to return for their End of Treatment and End of Study visits, they should have a safety follow-up call conducted 30 days after the last dosing visit, per [Section 7.2](#). The information collected is kept as source documentation. All SAEs reported during this time period must be reported as described in [Section 9.2](#) and the Site Operations Manual. Documentation of attempts to contact the subject should be recorded in the source documentation.

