7.2 Discontinuation of study treatment

Subjects may voluntarily discontinue study treatment for any reason at any time.

The investigator must discontinue study treatment for a given subject if, on balance, he/she believes that continuation would be detrimental to the subject's well-being.

Study treatment *must* be discontinued for an individual subject under the following circumstances:

- Withdrawal of consent
- An infusion reaction that is considered severe
- One or more symptomatic hypoglycemic events necessitating third party rescue and suspected to be related to study drug; if diabetes medication can be appropriately reduced, the study drug may be resumed after stabilization of FPG at the Investigator's discretion
- A serious adverse event (SAE) thought to be related to study drug
- Pregnancy: a positive urine pregnancy test after start of study treatment requires immediate interruption of study treatment until serum hCG is performed and found to be negative
- Any protocol deviation that results in a significant risk to the subject's safety
- Emergence of one or more adverse events that in the judgment of the investigator, taking into account the subject's overall status, prevent the subject from safely continuing in the study

Investigational treatment *may* be discontinued under the following circumstances:

- Breaking of the blind (inadvertently or for emergency reasons)
- Use of prohibited treatment as described in the protocol

Subjects who discontinue study treatment should **NOT** be considered withdrawn from the study UNLESS they withdraw their consent. They should return approximately 4 weeks after their last dose for the EoT visit (Visit 113). The EoS visit (Visit 199) should be scheduled

4 weeks after EoT. If they fail to return for these assessments for unknown reasons, every effort should be made to contact them as specified in [Section 7.4](#).

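### Section 5.1 asks women to agree to contraception only for the length of the study, about 14 weeks less than the six-month post-dose rule that opens the same section

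*Protocol*

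**What the plan says.** The six-month rule appears in three places in the protocol. The synopsis excludes women of childbearing potential "unless they are using highly effective methods of contraception during dosing and for 6 months after stopping of investigational drug". Exclusion criterion 2 in Section 4.2 requires highly effective contraception "during dosing and for 6 months after stopping of investigational drug". The first sentence of Section 5.1 sets the period as "during dosing and for 6 months after stopping study medication".

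The closing paragraph of Section 5.1 turns to what these women must be told and must agree to. They are to be warned of "unknown risks to the fetus if pregnancy were to occur during the study", and they are to agree that "they must adhere to the contraception requirement for the duration of the study". Neither statement mentions the six months after the last dose.

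Three other sections fix how long a study lasts:

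- Section 3.1 describes the "end of study visit (EOS) which will take place 12 weeks after the last study drug administration".
- Section 7.2 brings women who stop treatment early back about 4 weeks after their last dose for the end-of-treatment visit, with the end-of-study visit 4 weeks after that.
- Section 7.1 also has a trial-level definition: "Study completion is defined as when the last subject completes their Study Completion visit".

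**The concern.** The paragraph that governs disclosure and agreement gives a shorter period than the rule it is meant to put into effect. A site that took its wording from this paragraph would ask a woman to commit for less time than the protocol requires, and would describe fetal risk over a narrower window.

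The gap falls after the last scheduled contact. The assessment schedule (Table 8-1) ends at the end-of-study visit, so no later visit exists at which a misunderstanding could be noticed. In those weeks, adherence depends on what the woman was told and accepted at the start.

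The protocol's other instructions do not settle the matter. The introduction to Section 5 tells sites to inform and remind subjects of that section's restrictions, and Section 8.2 points them to Sections 4.2 and 5.1. A site following either instruction meets both periods in 5.1.

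**Working it through.** The check is date arithmetic on the protocol's own schedule.

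**Inputs**

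- Dosing: twelve doses, one every 4 weeks (Section 3.1). The last is at the Day 308 visit (Table 8-1).
- End-of-study visit for completers: Day 392 (Table 8-1).
- Early stoppers: about 4 weeks from last dose to end of treatment, then 4 weeks to end of study (Section 7.2).
- Required period after the last dose: six months (synopsis, Sections 4.2 and 5.1). The protocol does not convert this to days. I assume calendar months, which gives 181 to 184 days, with 183 as a midpoint.

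**Reproducing the protocol's interval**

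Eleven 4-week intervals separate the first and twelfth doses: 11 × 28 = 308, which matches the schedule. From last dose to end of study is 392 − 308 = 84 days, and 84 / 7 = 12 weeks. This agrees with Section 3.1.

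**Shortfall on the per-subject reading**

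Shortfall = six months − days from last dose to end of study.

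| | Last dose to end of study | Shortfall at 181 days | At 183 days | At 184 days | Share of six months elapsed at end of study (183 days) |
|---|---|---|---|---|---|
| Completer | 84 days | 97 days | 99 days (14.1 weeks) | 100 days | 84/183 = 46% |
| Early stopper | 28 + 28 = 56 days | 125 days | 127 days (18.1 weeks) | 128 days | 56/183 = 31% |

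Even if a month is counted as only 28 days, six months are 168 days. The shortfall is then 168 − 84 = 84 days (12 weeks) for completers and 168 − 56 = 112 days (16 weeks) for early stoppers.

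**Shortfall on the trial-level reading**

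Suppose the study is taken to end at the last subject's final visit, as in Section 7.1, and that this subject is a completer. Let x be the number of days by which a woman's last dose precedes that subject's last dose. Her agreed period after dosing is then 84 + x days, so

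shortfall = max(0, 183 − 84 − x) = max(0, 99 − x) days.

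The full 99 days apply only at x = 0. The shortfall disappears once x reaches about 99 days. On this reading each woman has a different period, and its length cannot be known when she consents.

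**The case against.** The strongest reply is that there is no real contradiction. The agreement sentence refers to the contraception requirement, and in a section with that title the phrase points back to the six-month rule. A woman who follows that rule also satisfies the closing sentence. The period is stated three times and is a condition of eligibility. Under Section 8.2 the sponsor supplies a proposed consent form, reviews the investigator's version, and must agree to changes before ethics submission. For the wrong period to reach a woman, a site would have to overlook the opening of the same section, and the form may well be correct. Section 3.3 adds that the 12-week visit covers the wash-out of exposure linked to anabolic effect, put at about 8 weeks.

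Much of this stands. The binding rule is unchanged, the consent form is unseen, and the route to harm is indirect. Three parts do not carry the argument:

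- The back-reference identifies what must be adhered to, but the sentence then sets its own time limit on adherence.
- The fetal-risk clause contains no back-reference. It simply confines the warning to the study.
- The wash-out statement concerns anabolic effect and not fetal safety. The sponsor chose six months and calls the fetal risk unknown, and the point here is only that the agreement should match that choice.

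The size of the gap does depend on how the study's end is read. The per-subject reading is the natural one, because it gives each woman a period that can be stated in advance.

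**Conclusion.** The concern holds. The closing paragraph of Section 5.1 states a shorter commitment and a narrower fetal-risk warning than the rule in the same section, in Section 4.2 and in the synopsis. The shortfall is about 14 weeks for completers and about 18 weeks for early stoppers. These figures assume calendar months and a study that ends at the subject's own final visit. On the trial-level reading the shortfall runs from about 14 weeks for the last completer down to zero for women dosed about 99 days or more before her.

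The practical weight is modest. The six-month rule remains in force, nothing shows that any woman was misinformed, and no statistical result is affected. It should still be corrected, because the inconsistent text is an operative safety instruction.

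**What to change.** In the last paragraph of Section 5.1:

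1. Replace the study-length limit on adherence with the period in the section's opening sentence: "during dosing and for 6 months after stopping study medication".
2. Extend the fetal-risk warning to pregnancy at any time in that same period.

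Then check that the consent form states the six-month period, both for the commitment and for the risk. Section 9.7 needs no edit, since it already makes any pregnancy after consent reportable without an end date.

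The cost is two phrases in one paragraph and a check of the consent form, with no change to design, visits, eligibility or analysis.

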5.2 Prohibited treatment

- Use of skeletal muscle anabolic agents in any form such as medications, hormones, over the counter products and nutritional supplements (other than protein) that are labeled as muscle anabolic agents.
- Anti-obesity medications, nutritional supplements, dietary interventions other than described in the protocol, or over the counter products for weight loss.
- Chronic systemic steroid treatment or systemic steroids for > 7 consecutive days for worsening of an underlying condition are not allowed during the study and within 4 weeks of screening.
- Any anti diabetic medication other than metformin or DPP4 inhibitor agent. Injectable drugs such as exenatide or pramlintide are prohibited; insulin is allowed for up to one week at a time to correct for acute hyperglycemia.
- Any product or medication known or suspected to cause weight gain, unless it is a stable anti-depressant therapy for at least 3 months before screening.

5.3 Dietary restrictions and smoking

Patients will be counseled to follow a modest calorie restricted diet with a daily deficit of approximately 500 kcal and approximately 45-50% calories from carbohydrate, 20-25% from protein and 30% from fat intake throughout the study, in keeping with guidelines for daily recommended protein intake (at least 1.2 g/kg/body weight) for anabolism ([WHO guidelines 2015](#)). The amount of calories will be determined by a dietitian or physician for every patient according to their height, weight and calculated basal metabolism. A copy of

the diet with content and nutritional information will be provided to the Sponsor prior to study start upon request.

Once enrolled and throughout the study period, site personnel will query study patients to determine if there has been a change in dietary habits and to encourage dietary intake that will promote weight loss. Dietary monitoring will occur via:

- Monthly dietary counseling visits at which time a 24 hour recall will be obtained
- Collection of 3-day food records at 3 time points during the study
- One telephone or in-person contact per month, approximately midway between counseling visits, to obtain a 24-hour dietary recall and reinforce lifestyle intervention.

Subjects will be advised to consume a daily multivitamin/multimineral supplement.

Smoking is discouraged but not prohibited for participation in this trial. Patients should refrain from smoking for one hour prior to study visits and during the study visits.

On Day 1, no breakfast will be provided. Meals should be similar in caloric content and macronutrient distribution for all patients on the day of dosing.

5.4 Other restrictions

On any visit day where fasting is required, patients should withhold their anti-diabetic medication until after study blood draws are completed, ideally before 10 AM. Additionally, patients should restrict alcohol consumption for 24 hours prior to visits at which the lipid profile will be assessed.

6 Treatment

6.1 Study treatment

Details on the requirements for storage and management of study treatment, and instructions to be followed for subject numbering, prescribing/dispensing and taking study treatment are outlined in the Site Operations Manual and Pharmacy Manual.

Refer to [Section 5.3](#) ‘Dietary restrictions and smoking’ for details of dosing and food intake.

6.1.1 Investigational treatment and control drugs

The investigational drug, bimagrumab, 150 mg LIVI (liquid in vial), will be prepared by Novartis and supplied to the Investigator site as open labeled bulk medication. Study drug preparation will be detailed in a separate pharmacy manual. Placebo will be a D5W infusion supplied by the site.

Table 6-1 Overview of study medication

Study drug name	Formulation	Appearance (e.g., approximate size, color, etc.)	Packaging	Provided by
BYM338 (bimagrumab)	liquid in vial	water infusion	open labeled bulk medication	Novartis
Placebo	Liquid	water infusion		Site

Study drugs must be received at the study site by a designated person, handled and stored safely and properly, and kept in a secure location to which only the Investigator and designated staff have access. Upon receipt, the study drugs should be stored according to the instructions specified on the drug labels. Storage conditions must be adequately monitored and appropriate temperature logs maintained as source data. Appropriate documentation of the patient specific dispensing process must be maintained. Bulk medication labels will be in the local language, will comply with the legal requirements of each country, and will include storage conditions for the drug but no information about the patient.

Note: To maintain the blind, the investigational treatments will be prepared by an unblinded pharmacist/designee, the bags will be covered by an opaque sleeve, and the investigational treatment will **only be administered by study personnel blinded to patient treatment allocation**.

All drug supplies are to be used only for this protocol and not for any other purpose. Unless specifically instructed by Novartis, the Investigator must not destroy any drug labels, or any partly used or unused drug supply. Only after receiving a written authorization by Novartis, the Investigator/designee will send all the unused and partly used drug supplies, as well as the empty containers, to the address provided at the time of authorization for destruction.

Sponsor qualified medical personnel will be readily available to advise on trial related medical questions or problems.

6.1.2 Additional study treatment

Not applicable.

6.2 Treatment arms

Patients will be assigned to one of the following 2 treatment arms in a ratio of 1:1.

Study treatments are defined as:

- Bimagrumab 10 mg/kg up to maximum 1200 mg, every 4 weeks (12 doses)
- Placebo, every 4 weeks (12 doses)

6.3 Permitted dose adjustments and interruptions of study treatment

Dose adjustments are not permitted.

6.4 Background therapy dose adjustments

Adjustments of T2D background therapy are allowed, according to the standard of care, but are restricted to the following:

- Either increased or decreased dosage, or discontinuation, of current medication is allowed under the guidance of a medical professional;
- The add-on of a second medication is allowed but restricted to metformin or DPP4-inhibitor;
- Insulin, as an acute treatment for severe or uncontrolled hyperglycemia, such as during an acute illness, is allowed but restricted to one week only;

The Investigator must emphasize to the subjects the importance to communicate ANY change in the background medication. In particular, the Investigator must inform the subjects that ANY change in the anti-diabetes medication that IS NOT LISTED above, will cause the subject to discontinue study treatment. Any modification to the background therapy during study participation must be reported by the Investigator.

6.5 Treatment assignment and randomization

Treatment is assigned by stratified randomization for two strata based on the patient's baseline BMI. The strata have the following randomization numbers:

- BMI between 28.0 kg/m² and 33.0 kg/m² (inclusive): 5101 – 5150
- BMI between 33.1 kg/m² and up to 40.0 kg/m² (inclusive): 5201 – 5250

The randomization number is used to identify which strata the patient belonged to at randomization and which treatment the patients have been randomized to receive.

The Patient number assigned to a patient at screening remains the unique identifier for the patient throughout the study. For information on patient numbering, please see 'Subject numbering' section in the SOM.

The randomization numbers will be generated using the following procedure to ensure that treatment assignment is unbiased and concealed from subjects and investigator staff. A randomization list will be produced by, or under the responsibility of, Novartis Drug Supply Management using a validated system that automates the random assignment of treatment arms to randomization numbers in the specified ratio.

BMI was selected as a stratification parameter as it is an important predictor of response on parameters of body composition/body weight and HbA1c (internal data). The expected median value for BMI in this patient population is 33 kg/m² (internal data); therefore, 2 strata above and below/inclusive of the median will ensure a balanced representation of patients between placebo and active drug in each strata, i.e. strata of approximately similar size between the 2 arms. Equal size strata will not be enforced, but a minimal size of 10 will be required for the smaller stratum in order to ensure adequate precision of treatment effect estimation in both strata.

The randomization scheme for patients will be reviewed and approved by a member of the Randomization Office.

Follow the details outlined in the Site Operations Manual regarding the process and timing of treatment assignment and randomization of subjects.

